[figure not shown]

[figure not shown]
**A Research on the Clinical Significance of Sentinel Lymph Node
Imaging Combined With Imaging Examination in Pelvic and
Peritoneal Lymphadenectomy for Endometrial Carcinoma**

2019.02.01

Study objectives The primary objective of this study is to identify the specific number and percentage of pelvic and abdominal lymph nodes that are invaded by metastatic endometrial carcinoma, and to calculate the coincidence rate of lymph node imaging and pathological examination. By setting up the control group and experimental group, we plan to find out whether pelvic and abdominal lymphadenectomy would exert positive effect on patients with endometrial carcinoma.

Trial design This is a prospective interventional trial. After signing of informed consent, the electronic medical data of patients with endometrial carcinoma will be collected in this study. The specific number and percentage of pelvic and abdominal nodes that are invaded by tumor cells will be calculated. By combining the imaging results and pathological test, we plan to obtain the coincidence rate of three tests. Finally, we would randomize patients into the control group and the experimental group as to receive the pelvic and peritoneal lymphadenectomy. When their postoperative data such as the reoccurrence rate and the five year survival rate are compared, the effect of pelvic and peritoneal lymphadenectomy on the prognosis of endometrial carcinoma are drawn.

Sample size The planned sample size was based on data from a previous study, in which the standard deviation was 5. We assumed an one-tailed α error of 0.05 and a sampling error of 1.0. We propose to enroll 70 participants including 35 patients in the control group and the others in the experimental group, and allow for a dropout rate of 10% for an effective sample size of 60.

Inclusion criteria

1. Volunteer to participate in the study with informed consent;
2. Females aged 10-90 who are confirmed with endometrial carcinoma and are willing to receive primary non-reserved fertility function surgery.

Exclusion criteria

1. Pregnancy, lactation, postmenopause, or planned pregnancy within two years;
2. Suspected or identified as other tumors of genital tract;
3. History of hyperparathyroidism, infectious diseases (tuberculosis, AIDS), autoimmune diseases, or digestive system diseases (malabsorption, crohn disease and dysentery);
4. Other diseases or heavy injuries that will interfere with the results;

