5. Simultaneous participation in another clinical study with investigational medicinal product(s) or researcher thinks the subjects are not suitable for this trial.

Withdrawal Subjects must be withdrawn from the study when one of the following criteria occurs:

1. At their own request. At any time during the study and without giving reasons, a subject may decline to participate further. The subject will not suffer any disadvantages as a result;
2. In the investigator's opinion, continuation of the study treatment would be harmful to the subject's health;
3. Obvious non-compliance;

4. Lost to follow-up;
5. Pregnancy;
6. Other medical or surgical treatments of endometrial carcinoma.

Safety assessments

Safety will be assessed by renal and liver function test, electrolyte, routine blood test. Other indicators are detected during the operation and rehabilitation period. The occurrence of any adverse events in participants will be recorded in the case report forms during each patient visit. We will withdraw patients who have severe adverse events, as it is unsafe for them to continue the trial. Meanwhile, we will give them relevant medical care and follow them up until the reaction has terminated.

Statistic analysis

The specific number and percentage of pelvic and abdominal lymph nodes that are invaded by tumor cells are collected. Multiple linear regression analysis was applied to evaluate the risk of lymphatic metastasis related to fourteen independent variables including four qualitative variables (hypertension, diabetes, diagnosis according to the FIGO staging system and the pathological tumor type) and eight quantitative variables (age, BMI, the number of lymph nodes, the interval between biopsy and operation, surgical time, surgical bleeding, postoperative anticoagulant time, preoperative value of Hb, preoperative value of RBC and preoperative value of Hct). All statistical analyses were performed by SPSS 17.0 software package and the level of statistical significance was set at $P < 0.05$. All independent variables were incorporated into the model using the method of "Enter". Data are presented as mean \pm standard deviation. Meanwhile, we collect the lymph node imaging results and the pathological test results so as to investigate the coincidence rate of the three examinations by chi test. As to the analysis of the lymphadenectomy on patients, we would conduct corresponding statistical method to interpret the follow-up data.

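### Linear regression is planned for the risk of nodal metastasis with no outcome defined, and it is the wrong model family for any nodal outcome the plan allows

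*Combined protocol and SAP*

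**What the plan says.** The Statistic analysis section names one multivariable model: "Multiple linear regression analysis was applied to evaluate the risk of lymphatic metastasis related to fourteen independent variables". The predictors are "four qualitative variables (hypertension, diabetes, diagnosis according to the FIGO staging system and the pathological tumor type", followed by a list of quantitative variables. The text counts eight of these but lists ten; only ten gives the stated total (4 + 10 = 14, whereas 4 + 8 = 12). All predictors are forced in together, and significance is set at P < 0.05.

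The dependent variable is not defined. The nearest description of nodal data is in the same section: "The specific number and percentage of pelvic and abdominal lymph nodes that are invaded by tumor cells are collected". Study objectives says much the same, aiming to "identify the specific number and percentage of pelvic and abdominal lymph nodes that are invaded by metastatic endometrial carcinoma". No patient-level yes/no variable is named. The plan mentions no transformation, robust variance, or logistic or count model, and does not say how multi-category variables are coded.

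**The concern.** A risk is a probability. The data that could stand behind it are a yes/no status per patient, a count, or a percentage. None can fall below zero, and in each the variance moves with the mean. Ordinary linear regression assumes an unbounded outcome and errors of constant variance.

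Three things are at stake. Reported risks may be negative. The coefficients will not be the odds or risk ratios that readers expect from a risk-factor analysis. The P values used to name risk factors may not have the stated error rate. Because the outcome is undefined, it could also be chosen after the data are seen.

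**Working it through.** The plan gives no numerical result for this regression, so there is no figure to reproduce. The check asks how the stated model behaves under each outcome the documents allow.

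**Inputs from the documents.** Fourteen predictors, all entered; P < 0.05; effective sample size 60. The dropout arithmetic gives 70 × 0.9 = 63, not 60. This does not matter here: for a yes/no outcome at an assumed 15% rate with no true effects, 19.0% of fitted values are negative with 63 patients and 17.5% with 70.

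**Assumptions.** Node-positive rates, predictor distributions, correlations and effect sizes are not in the documents. All are assumed below.

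**Step 1: variance.** For a yes/no outcome with risk p, the variance is p(1 − p). At p = 0.05 it is 0.05 × 0.95 = 0.0475; at p = 0.45 it is 0.45 × 0.55 = 0.2475. The ratio is 0.2475 / 0.0475 = 5.2, so constant variance fails whenever a real risk factor exists.

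**Step 2: negative fitted values.** Linear regression with an intercept and 14 predictors was simulated at n = 60. At assumed node-positive rates of about 10% to 17%, with one true risk factor, 24% to 32% of fitted values were below zero across yes/no and percentage outcomes. Over a wider assumed range of 5% to 30%, and including count outcomes, the share ran from about 37% at the lowest rate to about 9% at the highest. Where it was counted, 97% to 100% of simulated trials had at least one negative fit.

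**Step 3: error rate for a predictor with no effect.** The truth was logistic, with slope 1.5 on one normal risk factor, n = 60 and 14 predictors. The null predictor was rejected at P < 0.05 as follows:

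| Null predictor | Correlation with true factor (assumed) | Rejected |
|---|---|---|
| Right-skewed (lognormal) | +0.5 | about 10% to 12% |
| Right-skewed (lognormal) | −0.5 | about 2% to 3% |
| Right-skewed (lognormal) | 0 | about 5% |
| Normal | +0.5 or −0.5 | about 5% |

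A separate check let the null predictor's spread differ between high-risk and low-risk patients. Rejection was 11.4% when the spread was twice as large in the high-risk group and 1.9% when it was half as large. In other scenarios it stayed between 4.7% and 5.4% on average.

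**Step 4: would changing the link be enough?** Node-positive patients expected = 60 × rate; events per predictor = that number / 14.

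| Assumed rate | Node-positive patients | Per predictor |
|---|---|---|
| 5% | 3 | 0.2 |
| 10% | 6 | 0.4 |
| 15% | 9 | 0.6 |
| 20% | 12 | 0.9 |
| 30% | 18 | 1.3 |

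A plain logistic model with all 14 predictors would not be stable at any of these rates.

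**Step 5: coding.** Take three equal-sized tumor types with assumed risks 0.1, 0.4 and 0.1. Coded 1, 2, 3, the slope is (−1 × 0.1 + 0 × 0.4 + 1 × 0.1) / 2 = 0. With the second and third codes swapped, it is (−1 × 0.1 + 1 × 0.4 + 0 × 0.1) / 2 = 0.15. One numeric code would therefore give a result that depends on an arbitrary order.

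**The case against.** The strongest reply has four parts.

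- **P values.** A reader might infer that linear regression makes P values too small here. The documents do not support that. Reversing the sign of one assumed correlation turns too many false positives into too few, and most predictors stay near 5%. No predictor distribution, correlation or node-positive rate is given, so the direction is unknown. This part of the reply stands.
- **Outcome.** The plan never says the outcome is yes/no, and it never says most values are zero. That is correct, but it does not rescue the model, because the number and percentage of invaded nodes are also bounded at zero with non-constant variance. A linear model with robust standard errors could be argued for, but the plan names no robust variance, and negative fitted risks would remain.
- **Coding.** A reader might infer that tumor type is entered as one numeric code. The total of fourteen counts variables, not model terms, and does not exclude indicators. What stands is only that the coding is unstated; the same gap would matter in a logistic model.
- **Importance.** The primary objective concerns the number and percentage of invaded nodes and the agreement of imaging with pathology, and the randomised comparison is separate. None of these uses the regression. This stands and lowers the severity.

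**Conclusion.** The point holds as a criticism of the model family and of the undefined dependent variable. Linear regression is the stated method, and no outcome the documents allow suits it. With about 60 patients and 14 predictors, roughly a quarter to a third of fitted values would be negative at assumed node-positive rates of about 10% to 17%. The error rate for a null predictor can range from about 2% to about 12% in the correlation scenarios simulated. Those figures depend on the assumed rates, correlation and skewness; the mismatch between model and outcome does not.

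A claim that the plan's risk-factor P values are inflated in general goes further than the documents allow, as does a claim that the trial's main result is invalid. Severity: should be fixed before analysis.

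**What to change.** Replace the regression sentences in Statistic analysis with text to this effect:

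- The outcome is at least one pathologically positive node (yes/no) for each patient with nodal pathology.
- It is analysed by Firth-penalised logistic regression, reporting odds ratios with 95% profile-likelihood intervals.
- A short, prespecified predictor list replaces the forced 14-variable model, since assumed rates of 5% to 30% give only about 3 to 18 node-positive patients.
- FIGO diagnosis and tumor type are entered as indicators with a stated reference category, merging small categories.
- If the number of positive nodes is also modelled, a count model with robust standard errors is used as a secondary analysis.

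Shortening the list is part of the fix. In simulation, Firth regression rejected a null variable in about 4% of trials with 3 predictors, but in only 1.2% to 3.4% with all 14, so penalisation alone leaves a conservative test.

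The cost is revised wording and a routine outside the SPSS 17.0 linear regression menu. Intervals will be wider and fewer variables will reach significance. Patients and data collection are unaffected.

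### Preoperative Hb, RBC and Hct are forced together into one linear model of about 60 patients with no provision for their collinearity, so a real blood-count effect is likely to be missed or given an unstable sign

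*Combined protocol and SAP*

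**What the plan says.** Under Statistic analysis in the combined protocol and SAP, "Multiple linear regression analysis was applied to evaluate the risk of lymphatic metastasis". The predictors are described as "fourteen independent variables including four qualitative variables". The quantitative list ends with "preoperative value of Hb, preoperative value of RBC and preoperative value of Hct". The text announces eight quantitative variables but names ten, and 4 + 10 gives the stated fourteen.

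On model building the section says "All independent variables were incorporated into the model using the method of" Enter, which in SPSS is forced entry without selection. Significance is set at P < 0.05. The section mentions no tolerance or variance inflation check, no choice of one red-cell measure, no joint test and no shrinkage.

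Under Sample size the plan reads "We propose to enroll 70 participants including 35 patients in the control group", and it goes on to "allow for a dropout rate of 10% for an effective sample size of 60". It does not say which patients enter the regression, and it does not tie the sample size to that model.

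**The concern.** Hb, RBC and Hct all describe the preoperative red-cell mass. By definition their ratios are the red-cell indices: Hct/RBC is mean cell volume, Hb/RBC mean cell haemoglobin, and Hb/Hct mean cell haemoglobin concentration. Once RBC and Hct are held fixed, what is left of Hb is mainly variation in those indices. The fitted Hb coefficient then no longer answers the natural question of whether a lower haemoglobin goes with nodal metastasis. The plan states no interest in cell indices.

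Forced entry makes this the prescribed analysis. Each of the three coefficients is adjusted for two overlapping measures, so its standard error grows, its sign becomes unstable and its test loses power. A reader who sees three non-significant rows could conclude that preoperative blood count is unrelated to metastasis when the model could hardly have shown otherwise.

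**Working it through.** **Inputs from the documents.** 70 enrolled, effective size 60, fourteen predictors, forced entry, significance level 0.05. The sidedness of the regression tests is not stated, so two-sided t tests are assumed.

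**The plan's figure of 60.** 70 × 0.90 = 63, not 60. Reaching 60 from 70 implies a loss of 1 − 60/70 = 14.3%. This does not matter here, because the power figures below agree to within 0.1 percentage point with 63 patients. I use 60.

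**Model size.** 60/14 = 4.3 patients per predictor. Residual df are 60 − 14 − 1 = 45, or 60 − 12 − 1 = 47 with one blood-count term. If FIGO stage or tumour type needs dummy variables, residual df fall further.

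**Assumed input.** The documents give no correlations among the three measures, so four scenarios span a range.

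**Variance inflation.** With a = r(Hb,Hct), b = r(Hb,RBC) and c = r(RBC,Hct), let D = 1 + 2abc − a² − b² − c². Then VIF(Hb) = (1 − c²)/D, VIF(RBC) = (1 − a²)/D and VIF(Hct) = (1 − b²)/D. The standard error grows by √VIF.

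For the first scenario, D = 1 + 0.624 − 0.64 − 0.36 − 0.4225 = 0.2015. So VIF(Hb) = 0.5775/0.2015 = 2.9, VIF(RBC) = 0.36/0.2015 = 1.8 and VIF(Hct) = 0.64/0.2015 = 3.2.

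| a, b, c (assumed) | VIF Hb / RBC / Hct | SE multiplier Hb / RBC / Hct |
|---|---|---|
| 0.80, 0.60, 0.65 | 2.9 / 1.8 / 3.2 | 1.7 / 1.3 / 1.8 |
| 0.90, 0.70, 0.75 | 5.3 / 2.3 / 6.2 | 2.3 / 1.5 / 2.5 |
| 0.95, 0.80, 0.85 | 10.3 / 3.6 / 13.3 | 3.2 / 1.9 / 3.7 |
| 0.97, 0.85, 0.88 | 16.9 / 4.4 / 20.8 | 4.1 / 2.1 / 4.6 |

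**Power for Hb.** Suppose Hb carries the effect, at a size that gives 80% power when it is the only blood-count term. With 47 df this needs a noncentrality of 2.86. With all three entered, the noncentrality becomes 2.86/√VIF(Hb), tested on 45 df. In the first scenario it is 2.86/1.69 = 1.69. Power across the four scenarios is 38%, 23%, 14% and 10%.

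**Joint test.** A 3-df F test of the three terms on 45 df has noncentrality 2.86² = 8.18, which gives about 62% power in every scenario.

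**Simulation check.** 4,000 replicates per scenario, 60 patients, fourteen predictors, true Hb effect 0.4 residual SD per SD of Hb:

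| Hb-Hct correlation | Hb significant, only blood-count term | Hb significant, all three entered | Any of the three significant | Hb sign wrong | Joint test significant |
|---|---|---|---|---|---|
| 0.80 | 77% | 35% | 40% | 6% | 59% |
| 0.90 | 76% | 21% | 27% | 13% | 58% |
| 0.95 | 75% | 13% | 19% | 21% | 58% |
| 0.97 | 77% | 10% | 16% | 25% | 59% |

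The standard error of a covariate unrelated to the blood count stayed at about 0.15 throughout.

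**The case against.** The strongest reply is that collinearity breaks no assumption of the model. The coefficients remain unbiased, each P value keeps its meaning as a test of one measure given the other two, and the wider standard error reports the imprecision honestly. That stands. A reader might infer that the P values cannot be interpreted, or that none of the three coefficients can be estimated usefully. The figures do not support either. RBC's VIF stays below 5 in every scenario, and at the mild end all three are only about 2 to 3.

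The correlations are not in the documents, and the plan does not say that the three values come from one blood sample. That also stands, and it is why a range is shown. For an Hb effect, though, even the mildest scenario leaves it more likely missed than found. The result is gentler if RBC carries the effect: the same method with VIF(RBC) gives 55% power at the mild end (noncentrality 2.86/1.34 = 2.14) and 26% at the other.

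The sample is uncertain too. Most listed variables are measured around surgery, so up to 70 patients might contribute. There could be fewer if one arm has no node dissection, which the design text leaves unclear.

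A reader might also want to add an events-per-variable argument. It does not belong here. It is a criterion for a binary outcome, the plan specifies linear regression, and the documents give no node-positive rate. Nor does the fix do much for general overfitting: dropping two terms moves 60/14 = 4.3 patients per predictor only to 60/12 = 5.0.

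**Conclusion.** The point holds for the three separate blood-count coefficients and no further. As written, the plan forces overlapping measures into one model and offers no way of handling them. Under assumed Hb-Hct correlations of 0.80 to 0.97, an effective sample of 60 and two-sided tests at 0.05, an Hb effect that one term would detect with 80% power is detected with 38% down to 10%. In the simulated setting its sign is wrong in 6% to 25% of trials. How severe this is depends on correlations that the trial's own data would have to supply.

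It would be wrong to conclude that the whole regression, or the trial, is compromised. Collinearity among these three does not inflate the standard errors of the other predictors, and the joint blood-count effect remains testable. The stated objectives (nodal involvement, the coincidence rate and the effect of lymphadenectomy) do not rest on these coefficients. It is a minor point that is cheap to put right.

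**What to change.** Add one sentence to Statistic analysis, before data are seen: one of the three measures, for example Hb, enters the model, and the other two are reported descriptively. The documents give no reason to prefer Hb. What matters is that the choice cannot depend on which measure turns out significant.

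If the sponsor wants to keep all three, prespecify a joint 3-df test of the blood-count terms, report their variance inflation factors and do not interpret the separate coefficients. In the setting above that test has about 62% power, against 80% for a single term that carries the effect.

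The first option needs no extra data or patients. Its downside is that the two dropped measures get no separate adjusted coefficients.

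### The only inference planned for the coincidence rate is an unspecified chi test, which in its ordinary forms neither estimates agreement nor shows missed node-positive cases

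*Combined protocol and SAP*

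**What the plan says.** Study objectives makes it part of the primary objective to "calculate the coincidence rate of lymph node imaging and pathological examination", which names two examinations. Trial design speaks of three: "By combining the imaging results and pathological test, we plan to obtain the coincidence rate of three tests". Statistic analysis says "we collect the lymph node imaging results and the pathological test results" and that the purpose is to "investigate the coincidence rate of the three examinations by chi test". That is the whole analysis of this quantity.

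Lymph node imaging and pathology are therefore named in general terms, but the three examinations are not listed. The title's wording, "Imaging Combined With Imaging Examination in Pelvic and", suggests sentinel node imaging, a further imaging examination and pathology, by inference only.

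Not stated for the coincidence rate: the null hypothesis, the form of chi-square, whether the unit is the patient or the node, what coincidence means among three tests, and any confidence interval. The general presentation rule ("Data are presented as mean" and standard deviation) does not suit a proportion. The sampling error of 1.0 under Sample size is not tied to this rate.

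**The concern.** The examinations are made on the same patients or nodes, so their results are paired. The objective asks how well imaging matches pathology, which is an estimation question. A chi-square P value answers another one: whether two results are associated at all, or whether two rates are equal.

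The title places imaging in the context of lymphadenectomy, where a missed metastasis and a false alarm are different errors. The raw coincidence rate adds them together, and no planned output separates them. The trial could report a high rate and a very small P value and still leave the reader unable to say what share of node-positive patients imaging found, or how precisely that is known. Leaving the variant, unit and examinations open also allows them to be chosen after the data are seen, on a primary objective.

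**Working it through.** **Inputs.** The plan gives no expected agreement, sensitivity, kappa or precision for this rate, so there is no figure of its own to reproduce. From the plan I take only the effective sample size: "allow for a dropout rate of 10% for an effective sample size of 60". (70 × 0.9 is 63, not 60. That is a separate matter and nothing here depends on it.) All cell counts below are assumptions.

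**Notation.** a = both positive, b = imaging positive only, c = pathology positive only, d = both negative, N = 60.

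**1. What Pearson tests.** χ² = N(ad − bc)² / [(a+b)(c+d)(a+c)(b+d)]. Kappa = (p_o − p_e)/(1 − p_e), and p_o − p_e = 2(ad − bc)/N². Both are zero exactly when ad = bc, so the null is kappa = 0. The square removes the sign: a/b/c/d = 8/2/2/48 (agreement 56/60 = 93.3%) and 2/48/8/2 (agreement 4/60 = 6.7%) both give χ² = 34.66, P = 3.9 × 10⁻⁹.

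**2. One cohort, 54/60 agreement, 12 pathology-positive.** The six errors are divided between missed and false positives.

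| a/b/c/d | Sensitivity | χ² | Pearson P | Kappa |
|---|---|---|---|---|
| 12/6/0/42 | 12/12 | 35.00 | 3.3 × 10⁻⁹ | 0.74 |
| 7/1/5/47 | 7/12 | 26.29 | 2.9 × 10⁻⁷ | 0.64 |
| 6/0/6/48 | 6/12 | 26.67 | 2.4 × 10⁻⁷ | 0.62 |

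First row: 60 × (12 × 42)² / (18 × 42 × 12 × 48) = 35.00; p_e = (18 × 12 + 42 × 48)/3600 = 0.62; kappa = 0.28/0.38 = 0.74. Last row: 60 × (6 × 48)² / (6 × 54 × 12 × 48) = 26.67; p_e = 0.74; kappa = 0.16/0.26 = 0.62.

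**3. Other numbers of positives, same 54/60.**
- 18 positives: sensitivity runs from 18/18 to 12/18, with P between 5 × 10⁻¹⁰ and 5 × 10⁻⁹.
- 6 positives: the test does respond. Sensitivity 6/6 to 1/6 gives P from 2 × 10⁻⁷ to 0.055; at 0/6 there are no imaging positives and χ² is undefined.

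**4. Imaging that calls everyone negative.** With 12 of 60 positive, coincidence is 48/60 = 80%. At 10% or 30% node-positive it is 90% or 70%.

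**5. Paired tests.** McNemar's test uses only b and c. Against pathology, the first and last rows of the table have discordant counts 6:0 and 0:6, and both give exact P = 2 × 0.5⁶ = 0.031. With 5/5/5/45, half the positives are missed and P = 1. Neither result estimates agreement.

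**6. Unpaired comparison of two methods.** Coincidence of 54/60 against 48/60 gives P = 0.125. Exact McNemar gives 0.031 to 0.238, depending on how far the two methods' errors overlap, and only complete overlap falls below 0.05. This effect is modest.

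**7. Precision (Clopper-Pearson 95%).** Agreement 54/60: 79.5–96.2%. Sensitivity 5/6: 36–99.6%; 10/12: 52–98%; 15/18: 59–96%.

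**8. If nodes are the unit.** Design effect = 1 + (m − 1) × ICC. With 10–30 nodes per patient and ICC 0.05–0.30 (both assumed) it runs from 1 + 9 × 0.05 = 1.45 to 1 + 29 × 0.30 = 9.7. The half-width for a 90% rate is 1.4–2.4 points if nodes are treated as independent and 2.2–4.6 points if clustering is respected.

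**The case against.** **The test is not the estimator.** The plan says it will calculate the rate, so a descriptive proportion is intended. This stands. What is missing is its definition among three tests, its interval, and the split of errors.

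**Chi test may mean McNemar or Cochran's Q.** Both are valid for comparing paired rates, so it would be too strong to call the test wrong under every reading. This stands too, but neither form estimates agreement or sensitivity, so the gap remains whichever is meant.

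**A reader might infer that two imaging tests in this trial could share the same coincidence rate, Pearson P and kappa while one finds every positive patient and the other half.** Tables 6/6/0/48 and 6/0/6/48 do match on all three (90%, 2.4 × 10⁻⁷, 0.62). They have 6 and 12 pathology-positive patients, however, and two tests read against one pathology result in the same patients share a single number of positives. With that number fixed at 12, the two extremes differ in P and in kappa. The supportable point is the weaker one: every P value is tiny across a wide range of sensitivity.

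**A reader might also infer that the plan names no examinations, or that standard deviation is its only statement of precision.** Neither is right: imaging and pathology are named, and Sample size gives a sampling error. What is absent is a list of the three examinations and a precision tied to this rate.

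**The counts are assumed.** True, because the plan gives none. The properties of the tests do not depend on them; the sizes shown do.

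**Conclusion.** The concern holds as underspecification of a primary-objective analysis, together with a named test that does not answer the question in any ordinary form. The general argument needs only that the examinations are paired. Its size rests on assumed tables of 60 patients: at 20–30% node-positive with 90% agreement, Pearson P is below 10⁻⁶ whether imaging finds all positives or only a half to two-thirds of them. At 10% node-positive the test is more informative, so the insensitivity is not universal.

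Using 60 may be optimistic. Trial design randomises patients with respect to lymphadenectomy and does not make clear whether both groups will have nodal pathology. If fewer than 60 do, every interval widens. The documents do not support a claim that the planned rate itself is invalid, or that the trial's conclusions would necessarily be wrong.

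**What to change.** Replace the chi test as the inference for coincidence. In the SAP:

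- List the three examinations and state the unit of analysis.
- State whether three-way coincidence means all three agreeing or pairwise agreement.
- Take pathology as the reference, restrict the denominator to patients with a pathology result, and report that number.
- For each imaging test, and for the combination under a rule stated in advance, report overall agreement, sensitivity, specificity and negative predictive value with exact 95% confidence intervals at patient level. Kappa is optional.
- Use a patient-clustered variance for any node-level figure.
- Keep McNemar's test or Cochran's Q only for comparing paired rates between tests, including correct/incorrect results against pathology.

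The cost is SAP wording and a little more analysis of imaging and pathology results the plan already collects. The drawback is that the limited precision becomes visible, above all for sensitivity (52–98% at 10/12).
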